20.4. Adverse Event and Serious Adverse Event Recording and Reporting

AEs and SAEs will be recorded from signing of the ICF through completion of the final study visit. The investigator is required to record the AE or SAE regardless of the severity of the event or its relationship to study treatment. Prior to the Baseline Visit/Day 1, only AEs and SAEs related to study procedures will be recorded. The investigator must follow up on all AEs and SAEs reported until the event has resolved or stabilized or at such time the

investigator refers the subject to a nonstudy physician. The investigator will document the further follow-up information in the subject's source document.

During the period specified above, the investigator will:

Record all AEs and SAEs from the signing of the ICF through the completion of the End of Study/Early Termination visit.

Report all SAEs on an SAE Report Form to Global Pharmacovigilance or designee.

Report all pregnancies to the Global Pharmacovigilance or designee contact-on the Pregnancy Surveillance Form.

Submit any Expedited Safety Report or Suspected Unexpected Serious Adverse Reaction from Global Pharmacovigilance or designee to the IRB/IEC.

The reporting requirements for AEs are summarized in [Table 4](#).

Table 4: Reporting Requirements for Adverse Events

Seriousness	Reporting Time	Type of Report
All Serious	Within 24 hours of first knowledge of event	Initial report on the SAE Form, appropriate eCRF, and source document
	Within 24 hours of receipt of follow-up information	Follow up report on the SAE Form, appropriate eCRF, and source document
Nonserious	Per case report form submission procedure	Appropriate eCRF and source document

Adverse Events

Adverse events can be reported spontaneously or elicited during open-ended questioning (ie, "How have you been feeling since your last visit?"), examination, or evaluation of a subject. Signs and symptoms must be recorded using standard medical terminology. For subjects incapable of giving consent, the legally acceptable representative may provide information regarding the subject's status.

All fields on the AE CRF page should be completed for each event with a full description of the event and date of onset/start and resolution/stop. A medical diagnosis if known, should be recorded in lieu of each individual sign and symptom associated with the diagnosis and experienced by the subject. If no medical diagnosis is known, the term used by the subject to describe the event or signs noted by the site personnel should be recorded.

Serious Adverse Events

Initial Reporting

Serious adverse events (based on FDA/ICH definition of an SAE) require immediate reporting to Mallinckrodt Global Pharmacovigilance or designee.

For all SAEs, the investigator, or designee, must complete the SAE Report Form with the minimum information required by FDA and ICH and fax it to Mallinckrodt Global Pharmacovigilance or designee within 24 hours of first knowledge of the event even if the experience does not appear to be related to the IMP.

The investigator, or designee, will receive acknowledgement of receipt of the SAE Report Form from Mallinckrodt Global Pharmacovigilance or designee.

Should the investigator or designee have any difficulty in sending the SAE Report, they may contact Mallinckrodt Global Pharmacovigilance or designee based on the information in the Study Operations Manual.

If there is any doubt about whether the information constitutes an SAE, the information is to be treated as an SAE.

The investigator(s) or designee is required to submit the any Expedited Safety Report or Suspected Unexpected Serious Adverse Reaction to the responsible IRB/IEC.

The sponsor will ensure that any Expedited Safety Report or Suspected Unexpected Serious Adverse Reaction is submitted to the FDA and other regulatory agencies as appropriate.

Follow Up Reporting

The investigator or designee must complete an SAE Report Form for all follow-up information received and fax it to Mallinckrodt Global Pharmacovigilance or designee within 24 hours of receipt. The investigator(s) or designee will receive acknowledgement of receipt for each SAE Report Form from Mallinckrodt Global Pharmacovigilance or designee.

The investigator or designee is required to provide all related information/supporting documentation of an SAE until the SAE is resolved or stabilized or the subject has been referred to a nonstudy physician for follow-up treatment.

The investigator(s) or designee is required to submit the Safety Alert to the responsible IRB/IEC.

The sponsor will ensure that any Expedited Safety Report or Suspected Unexpected Serious Adverse Reaction is submitted to the FDA and other regulatory agencies as appropriate.

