14.6. Day 42 (\pm 2 Days) Follow-up Visit 2/Early Termination Procedures/Assessments

The following procedures will be completed at Study Day 42 (\pm 2 days) or whenever a subject terminates early from the study:

- MSIS-29, [REDACTED]
- Current medical condition review.
- Complete physical examination.
- FSS and EDSS.
- CGI-I.
- Weight.
- Vital signs.
- 12-lead ECG.
- Clinical laboratory tests.
- Serum pregnancy test.
- Diary review and study drug accountability (if appropriate, for early termination only).
- Adverse events and concomitant medications.

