19.3.2. Primary Safety Endpoint

The primary safety endpoint will be a summary of general safety profile, including adverse events (serious and nonserious), vital signs and laboratory assessments by study period and over the entire study.

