21. SUBJECT DISCONTINUATION OR WITHDRAWAL

21.1. Subject Withdrawal

Subjects who discontinue, or are withdrawn from the study for any reason, will be required to enter the follow-up period and have the Early Termination and Follow-up safety assessments (see [Section 14.5](#) and [Section 14.6](#)) to assess their continued well-being.

The reason for discontinuation will be recorded. A subject may be discontinued from the study for the following medical or administrative reasons:

Withdrawal by Subject

Subjects will be free to discontinue from the study at any time. Subjects who have received at least 1 dose of study drug but do not complete the study will not be replaced.

Lack of Efficacy

Subjects who undergo plasma exchange or receive IVIg following treatment with Acthar due to lack of efficacy will be considered treatment failures and will be withdrawn from the study.

Adverse Event

If a dosed subject suffers an AE that, in the judgment of the investigator, sponsor or MM, presents an unacceptable consequence or risk to the subject, the subject will be discontinued from further participation in the study.

Death

In the event that a subject dies during the study, death will be the reason for discontinuation.

Lost to Follow-up

Every effort should be used to maintain contact with subjects during their participation in the study. A subject may be considered lost to follow up if there is no response to 3 attempts to reach the subject by telephone and no response to a certified letter sent to the last known address of the subject. Efforts to contact the subject should be noted in source documentation.

Met Withdrawal Criteria

If a subject develops a condition that meets any of the exclusion criteria ([Section 12.2](#)) or fails to meet an inclusion criteria ([Section 12.1](#)) during the study that is not considered to be an AE or is noncompliant (eg, has a positive pregnancy during the screening or treatment periods or positive drug screening test), the subject will be discontinued from further participation in the study. Discontinuation is also mandated for safety and/or tolerability issues as outlined in [Section 15.3.1](#).

Other

If the above reasons are not applicable, please use the “Other” option and provide the appropriate reason for subject withdrawal.

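### Section 20.4 gives two end points for AE and SAE recording, and the Early Termination one conflicts with the follow-up that 21.1 requires of every withdrawn subject

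*Combined protocol and SAP*

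**What the plan says.** Four parts of the protocol bear on when recording ends.

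- **20.4, opening sentence:** "AEs and SAEs will be recorded from signing of the ICF through completion of the final study visit".
- **20.4, investigator task list:** "Record all AEs and SAEs from the signing of the ICF through the completion of the End of Study/Early Termination visit". SAE and pregnancy reporting to pharmacovigilance stand in the same list, under the same stated period.
- **14.6:** one set of procedures serves both Day 42 and Early Termination. They are done at Day 42 "or whenever a subject terminates early from the study". No minimum interval after the last dose is set.
- **21.1:** subjects who discontinue or are withdrawn for any reason "will be required to enter the follow-up period and have the Early Termination and Follow-up safety assessments", with references to 14.5 and 14.6. Both of those sections list AE collection.

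Subjects stopped for harm are on this path. Under 21.1, if an AE "presents an unacceptable consequence or risk to the subject, the subject will be discontinued from further participation in the study". The same section adds: "Discontinuation is also mandated for safety and/or tolerability issues as outlined in" 15.3.1.

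Safety and tolerability form one of the two primary objectives (10.1). The primary safety endpoint (19.3.2) covers adverse events, "vital signs and laboratory assessments by study period and over the entire study".

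**The concern.** A completer has new events recorded to Day 42, about four weeks after the last dose. Under the task-list line in 20.4, a subject who leaves early has recording closed at a visit held when they leave, possibly on the last dosing day. Section 21.1 then brings that subject back for assessments that include AE collection. A site could be asked to assess AEs at Day 21 after its stated recording duty has ended.

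What is at stake is the completeness of new-event data after an early stop, in a trial where safety is a primary objective. Section 19.6.1 summarizes treatment-emergent events by treatment group and names no adjustment for time observed. If early stops differed between arms and sites applied the Early Termination cut-off, the arms would be compared over unequal windows. Late SAEs in exposed subjects could also go unrecorded.

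**Working it through.** The plan gives no figure of its own here, so the check compares the sections and then does date arithmetic.

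**Step 1. Which end point applies to a withdrawn subject?**

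| Reading | Source | Recording ends |
|---|---|---|
| A | 20.4 task list with 14.6 | At the Early Termination visit, on the day of termination |
| B | 20.4 opening sentence with 21.1, if 14.6 is attended once, as the Early Termination visit | At the Day 21 visit (14.5) |
| C | 20.4 opening sentence with 21.1, if 14.6 is attended twice, at termination and again at Day 42 | At Day 42 |

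The phrase final study visit does not choose among these. Section 14.6 treats Day 42 and Early Termination as one visit, so Early Termination can itself be read as the final visit. Section 21.1 cites 14.6 without saying whether a withdrawn subject attends it once or twice.

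**Step 2. What is lost under reading A?** Sections 17.1 and 20.4 have reported AEs followed until resolved or stabilized (20.4 also allows referral to a nonstudy physician). Section 20.5 has AEs of special interest followed until resolution or return to baseline. So the event that caused the stop stays under follow-up. Two things are left without a recording duty:

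- new-onset AEs and SAEs after the Early Termination visit;
- AEs that change in severity or seriousness, because 20.3 closes the original entry and opens a new one.

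**Step 3. Size of the gap for one subject.** Inputs: 14 days of treatment and last visit at Day 42 (11.2), and Follow-up Visit 1 at Day 21 (14.5). Visit windows are ignored. The termination days are my assumption, with the Early Termination visit held that day and dosing continued until then, up to Day 14.

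Unrecorded share = (42 − e)/42, where e is the last day covered by recording.

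| Terminated on | A: Early Termination | B: Day 21 | C: Day 42 |
|---|---|---|---|
| Day 7 | (42 − 7)/42 = 35/42 = 83% | (42 − 21)/42 = 21/42 = 50% | 0% |
| Day 14 | (42 − 14)/42 = 28/42 = 67% | 21/42 = 50% | 0% |
| Day 21 | 21/42 = 50% | 21/42 = 50% | 0% |

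Off-drug recording for the Day 7 case is 7 − 7 = 0 days under A, 21 − 7 = 14 under B and 42 − 7 = 35 under C. A completer has 42 − 14 = 28.

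**Step 4. Size per arm.** With 33 subjects per arm (19.9), planned observation is 33 × 42 = 1,386 subject-days. Each Day 7 termination removes 35/1,386 = 2.5% under A, 21/1,386 = 1.5% under B and nothing under C. The number of early terminations is not given. The allowance in 19.9 of 3 subjects per arm is for failing to qualify for the mITT population. It is not a forecast of early stops, since a subject who leaves after a postbaseline EDSS still qualifies.

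**The case against.** The strongest defence is that 20.4 already has the right rule. Its opening sentence sets the period, and the task list sits beneath it as a summary of duties. With 21.1, the final study visit for a withdrawn subject is the last follow-up assessment, and 14.5 collects AEs there. Section 20.3 points the same way, since it leaves the stop date blank for AEs ongoing when the follow-up visit is completed. A site reading the protocol as a whole would record AEs at Day 21.

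That is a fair reading, and it means a reader should not infer that the protocol simply ends recording at Early Termination. It does not remove the conflict: the task list is the more specific instruction, and it names a different visit.

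A reader might also infer that subjects stopped for harm get the shortest safety follow-up. The documents do not support that. The event behind the stop is followed to resolution or stabilization, and 21.1 requires further assessments. Only the window for new or re-opened entries is in doubt, and it is in doubt for everyone who terminates early, whatever the reason.

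A third inference would be that AE rates in the Acthar arm are biased downward by a known amount. This fails too. Section 19.6.1 does not state the incidence metric, no split of early stops between arms is given, and a subject stopped for an AE already has that event recorded. The possible loss is in later, additional events.

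**Conclusion.** The point holds as an inconsistency with a practical consequence. Sections 14.6, 20.4 and 21.1 do not give one recording end point for withdrawn subjects. Under one of the stated end points, new and re-opened events after an early stop have no recording duty.

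For a Day 7 termination the unrecorded part of the 42-day window runs from 0% through 50% to 83%, depending on which reading a site applies. The upper figure assumes that nothing is recorded after termination, contrary to what 21.1 appears to intend. The lower one assumes that a Day 42 assessment takes place and picks up the interval since the previous contact. The arm-level effect is 0% to 2.5% of planned subject-days per Day 7 termination. The total, and any imbalance between arms, cannot be derived from the documents.

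It is worth correcting because safety is a primary objective and sites could apply the cut-off differently.

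**What to change.** In 20.4, replace the Early Termination cut-off with one end point for all dosed subjects, namely the end of the follow-up period that 21.1 already requires. Possible wording: *New and re-opened AEs and SAEs are recorded through Day 42 for every subject who received at least 1 dose of study drug, including those who have had an Early Termination visit, by telephone if needed, unless consent is withdrawn.* Use the same end point in the opening sentence and in the task list, so that SAE and pregnancy reporting share it.

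Then reconcile 14.6 and 21.1 with it. State whether a withdrawn subject attends 14.6 once or twice, and which contact counts as the last one for AE recording.

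This changes data recording only. The cost is amendment wording and a few extra contacts for subjects who leave early. The Day 14 assessments are already done by telephone (Table 1).

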20.5. Adverse Events of Special Interest

AEs of special interest for this study are outlined below. Adverse events of special interest will be followed until resolution or return to baseline.

- Elevated blood pressure (defined as systolic blood pressure ≥ 180 and diastolic blood pressure ≥ 100 mm Hg).
- Hyperglycemia (HbA1c $> 6.5\%$, or fasting plasma glucose > 126 mg/dL, or classic symptoms of hyperglycemia with random plasma glucose > 200 mg/dL).
- MedDRA System Organ Class infection/infestation of \geq moderate intensity.
- AEs considered possibly, probably, or definitely related to study drug treatment of \geq moderate intensity.
- Hy's Law cases (ALT > 3 x ULN, with total bilirubin > 2 x ULN, no initial signs of cholestasis [alkaline phosphatase within the reference range]), and no other reason can be found to explain liver injury).

20.6. Pregnancy Reporting

Certain information, although not considered an SAE, must be recorded, reported, and followed up as indicated. This includes the following:

Pregnancy exposure to an investigational medicinal product, except for exposure to prenatal vitamins. Subjects should not become pregnant during the study. If the subject becomes pregnant, study treatment must be discontinued immediately (subjects may complete follow-up visits). The investigator must report the pregnancy by submitting the appropriate form to Mallinckrodt Global Pharmacovigilance or designee within 24 hours of confirmation of a pregnancy (ie, positive serum pregnancy test result). The outcome of pregnancy (eg, spontaneous abortion, live birth, still birth, congenital anomalies, birth defects) must be reported by submitting the appropriate form to Mallinckrodt Global Pharmacovigilance or designee within 24 hours of the pregnancy outcome being submitted to the study site. If the pregnancy results in a live birth, a postdelivery follow-up will be performed at least 28 days after the baby is born and must be reported to Mallinckrodt Global Pharmacovigilance or designee within 24 hours of the study site becoming aware of the follow-up information. Both maternal and paternal investigational medicinal product exposures are collected.

If the female partner of a male subject becomes pregnant during the study, the site will forward the Pregnancy Notification form and the Pregnancy Report Fax cover page to Mallinckrodt Global Pharmacovigilance or designee, within 24 hours of being notified. The outcome of pregnancy (eg, spontaneous abortion, live birth, still birth, congenital anomalies, birth defects) must be reported by submitting the appropriate form to Mallinckrodt Global Pharmacovigilance or designee within 24 hours of the pregnancy outcome being submitted to the study site. If the pregnancy results in a live birth, a postdelivery follow-up will be performed at least 28 days after the baby is born and must be reported to Mallinckrodt Global Pharmacovigilance or designee within 24 hours of the study site becoming aware of the follow-up information.

21. SUBJECT DISCONTINUATION OR WITHDRAWAL

21.1. Subject Withdrawal

Subjects who discontinue, or are withdrawn from the study for any reason, will be required to enter the follow-up period and have the Early Termination and Follow-up safety assessments (see [Section 14.5](#) and [Section 14.6](#)) to assess their continued well-being.

The reason for discontinuation will be recorded. A subject may be discontinued from the study for the following medical or administrative reasons:

Withdrawal by Subject

Subjects will be free to discontinue from the study at any time. Subjects who have received at least 1 dose of study drug but do not complete the study will not be replaced.

Lack of Efficacy

Subjects who undergo plasma exchange or receive IVIg following treatment with Acthar due to lack of efficacy will be considered treatment failures and will be withdrawn from the study.

Adverse Event

If a dosed subject suffers an AE that, in the judgment of the investigator, sponsor or MM, presents an unacceptable consequence or risk to the subject, the subject will be discontinued from further participation in the study.

Death

In the event that a subject dies during the study, death will be the reason for discontinuation.

Lost to Follow-up

Every effort should be used to maintain contact with subjects during their participation in the study. A subject may be considered lost to follow up if there is no response to 3 attempts to reach the subject by telephone and no response to a certified letter sent to the last known address of the subject. Efforts to contact the subject should be noted in source documentation.

Met Withdrawal Criteria

If a subject develops a condition that meets any of the exclusion criteria ([Section 12.2](#)) or fails to meet an inclusion criteria ([Section 12.1](#)) during the study that is not considered to be an AE or is noncompliant (eg, has a positive pregnancy during the screening or treatment periods or positive drug screening test), the subject will be discontinued from further participation in the study. Discontinuation is also mandated for safety and/or tolerability issues as outlined in [Section 15.3.1](#).

Other

If the above reasons are not applicable, please use the “Other” option and provide the appropriate reason for subject withdrawal.

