15.3.1. Treatment Discontinuation

Treatment with study drug should be discontinued if any of the following occur:

- Development of accelerated hypertension (defined as systolic blood pressure \geq 180 *and* diastolic blood pressure \geq 100 mm Hg) that cannot be managed by the adjustment of concomitant medications such as antihypertensive medications.
- Development of congestive heart failure that cannot be managed by the adjustment of concomitant medications such as diuretics and antihypertensive medications.
- Development of diabetic signs/symptoms (ie, HbA1c $>$ 6.5%, or fasting plasma glucose $>$ 126 mg/dL, or classic symptoms of hyperglycemia with random plasma glucose $>$ 200 mg/dL).
- Subjects who undergo plasma exchange or IVIg due to lack of efficacy will be considered treatment failures and will be withdrawn from the study.
- Development of any other AE of at least moderate intensity and possibly, probably or definitely related to study drug that cannot be managed by the adjustment of concomitant medications.

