17.4. Physical Examination

A complete physical examination will be performed at the Baseline Visit and the Day 42/Early Termination Visit. The complete physical examination includes evaluation of the head, eyes, ears, nose, throat, neck (including thyroid), cardiovascular system (including assessment of heart, peripheral pulses, presence or absence of edema), lungs, abdomen (including liver and spleen, bowel sounds), lymph nodes, musculoskeletal system (including spine, joints, muscles) neurological system (including cranial nerves, reflexes, sensation, strength), skin, extremities and other conditions of note.

A limited physical examination, including evaluation of lungs, heart, abdomen, and extremities will be done at all other clinic visits.

The findings of the physical examinations will be recorded. Any change from the Screening Visit physical examination that is considered clinically significant by the investigator will be recorded as an AE.

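### A subject who only stops study drug may have no Day 42 EDSS, and the protocol does not say how that subject is then classified

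*Combined protocol and SAP*

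**What the plan says.** Section 15.3.1 is written as a rule about treatment: "Treatment with study drug should be discontinued if any of the following occur". Its triggers are accelerated hypertension, heart failure, diabetic signs, rescue by plasma exchange or IVIg, and other related adverse events of at least moderate intensity that cannot be managed. Only the plasma exchange/IVIg item adds that the subject leaves the study.

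Section 21.1 lists reasons for leaving the study. For adverse events that pose an unacceptable risk, and for subjects who meet withdrawal criteria, it says that "the subject will be discontinued from further participation in the study". Under the second of these it adds: "Discontinuation is also mandated for safety and/or tolerability issues as outlined in" Section 15.3.1. The same section opens by saying that anyone who discontinues or is withdrawn, for any reason, "will be required to enter the follow-up period and have the Early Termination and Follow-up safety assessments". It refers to 14.5 (Day 21) and 14.6 (Day 42), and gives the purpose as "to assess their continued well-being". Both of those visits list FSS and EDSS.

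Section 14.6 schedules its procedures at Day 42 "or whenever a subject terminates early from the study". Sections 17.4 and 20.4 use the same combined label: "A complete physical examination will be performed at the Baseline Visit and the Day 42/Early Termination Visit", and adverse events are recorded "through the completion of the End of Study/Early Termination visit".

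Under 19.10, a subject whose data do not permit classification on the primary endpoint is counted as a nonresponder. Under 19.2, one dose and a single EDSS after baseline are enough to enter the mITT population.

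**The concern.** Dosing lasts 14 days and the primary endpoint is read at Day 42. A subject who stops drug in the first two weeks can usually still be examined at Day 42, so the outcome is obtainable.

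The text leaves open whether it will be obtained. If the drug stop is handled as study withdrawal and the 14.6 visit is held at that moment, the last EDSS may fall weeks before Day 42. The subject stays in the mITT denominator because one earlier EDSS suffices. What happens next is not stated: the subject may be imputed a nonresponder, or the early-termination EDSS, taken under a visit that shares the Day 42 label, may be used to classify the subject. Two analysts could treat the same subject differently.

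Section 9.1 says that the pilot's response rates are meant to size a larger study, so a misstated rate carries forward. Section 9.5 lists raised blood pressure and altered glucose tolerance among the common Acthar reactions, and both are related to 15.3.1 triggers. Stops could therefore be more frequent on Acthar, but that is inference; the documents give no rates.

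**Working it through.** **1. The plan's own figures.** Section 19.9 assumes 30 mITT subjects per group and 90% Wilson intervals. For 18/30 = 60% the Wilson interval is 45.1% to 73.3%, half-width 14.1 points, as stated. The placebo interval of 15.7% to 41.5%, half-width 12.9, is reproduced with 8/30 (26.7%), the whole count used for the expected 25%; the plan calls it approximate. The allowance of 3 subjects per group covers only those who fail to enter mITT, not mITT subjects who lack a Day 42 EDSS.

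**2. The path through the text.**

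| Step | Section | Effect |
|---|---|---|
| Drug-stop trigger met | 15.3.1 | Treatment stops |
| Same triggers listed as reasons to leave the study | 21.1 | May be handled as withdrawal |
| Withdrawn subject goes to 14.5 and 14.6 | 21.1, opening | EDSS is due, described as safety follow-up |
| 14.6 visit may be held at early termination | 14.6 | Last EDSS can precede Day 42 |
| One EDSS after baseline is enough | 19.2 | Subject stays in the denominator |
| No Day 42 EDSS | 19.10, or no stated rule | Imputed nonresponder, or classified on the earlier EDSS |

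**3. Size if the subject is imputed a nonresponder.** Let k be the affected subjects per 30 and r the rate at which they would have responded at Day 42. Both are assumptions. The group's rate falls by k × r / 30.

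| k | r = 60% | r = 25% |
|---|---|---|
| 1 | 2.0 points (14% of 14.1) | 0.8 points (6%) |
| 2 | 4.0 points (28%) | 1.7 points (12%) |
| 3 | 6.0 points (43%) | 2.5 points (18%) |

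At k = 1 the expected Acthar rate as reported is 0.60 × 29/30 = 58.0% (90% Wilson 43.1% to 71.5%). For placebo at 25% it is 0.25 × 29/30 = 24.2%.

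**4. Size if the earlier EDSS is used.** One subject classified differently from the true Day 42 status moves the observed rate by 1/30 = 3.3 points. The move is up if an early improvement is later lost, and down if improvement comes after the early visit.

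**5. Effect on a later trial.** Assume two-sided 5%, 90% power and the pooled-variance formula, n = [1.960 √(2p̄(1−p̄)) + 1.282 √(p₁(1−p₁) + p₂(1−p₂))]² / (p₁−p₂)². For 60% vs 25%, p̄ = 0.425 and n = (1.370 + 0.838)² / 0.1225 = 39.8, so 40 per group. With one subject per group imputed, 58.0% vs 24.2% gives 43.

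The comparison depends on r. If affected Acthar subjects respond at 60%, the correct figure is 40 and the imputation adds 3 per group. If they respond at 25%, the Acthar rate with outcomes observed is (0.60 × 29 + 0.25)/30 = 58.8%. Against 25% that also needs 43, so the imputation changes nothing.

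**The case against.** The strongest answer is that 21.1 already deals with this. Its opening sentence covers withdrawal for any reason and cites both follow-up visits, which 11.2 places 21 and 42 days after the start of drug. If one early visit were enough, citing 14.5 would serve little purpose. This stands to the extent that the protocol does not simply drop follow-up after a drug stop, as a reader might infer from the withdrawal wording alone. It does not close the gap, because the sentence points to a visit that 14.6 allows to be held early.

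The wording of 15.3.1 also counts on the other side. Since only the plasma exchange/IVIg item mentions leaving the study, the remaining items can be read as stopping drug only. Section 21.1 then says that discontinuation is mandated without saying from what, under a heading about withdrawal. Both readings are open.

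A reader might infer that 17.7 and 20.6 contradict each other on pregnancy. Section 17.7 withdraws a subject who becomes pregnant during treatment, while 20.6 stops drug and lets follow-up visits be completed. The two can be reconciled through the opening of 21.1, so this is a place to align the wording and not separate evidence of lost outcomes. The labels in 17.4 and 20.4 likewise only repeat the combined visit name.

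Scoring a subject who stops for intolerance as a nonresponder is a legitimate choice. The plan does not make that choice, however: it names only plasma exchange and IVIg rescue as treatment failure. The primary endpoint is also reported in the Per-Protocol population, but that does not supply a Day 42 value for an early stopper. The separate analysis plan mentioned in 19.1 and 19.10 is not in the text reviewed. It could settle how an early-termination EDSS is classified, but it could not recover a Day 42 examination that was never done.

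**Conclusion.** The point holds as a conflict in the text and a missing rule. A site can comply with 14.6 and still leave a drug-stopper without a Day 42 EDSS, and the protocol does not say how that subject is classified. Either outcome can misstate the Day 42 rate although the examination could have been done.

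A reader might go further and conclude that the response rates are biased downward and that the Acthar rate cannot be inflated. The documents do not support a fixed direction. The fall follows only if the subject is imputed a nonresponder; if the early-termination EDSS is used, the error can go either way.

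Under imputation the size is 0.8 to 2.0 points per affected Acthar subject, for assumed response rates of 25% to 60%. That is small beside the planned 14.1-point half-width. The number affected is unknown. The upper figure assumes full planned efficacy after a partial course, and at the lower figure the later trial's size does not change. In an estimation-only pilot this is a worthwhile, inexpensive improvement. It does not invalidate the design.

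**What to change.** In 14.6 and 21.1, state that:

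- stopping study drug is not withdrawal from the study;
- a subject who stops drug for any reason other than withdrawal of consent attends the scheduled Day 21 and Day 42 visits, with EDSS/FSS by the blinded rater;
- an early-termination visit does not replace Day 42, and its EDSS is not used as the Day 42 value;
- subjects rescued before Day 42 with plasma exchange, IVIg or corticosteroids prohibited under 13.1 are counted as nonresponders.

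The last item prevents improvement after steroid rescue from being counted as response. Align 15.3.1, 17.7 and 20.6 with these statements. No stopping criterion changes.

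The cost is a protocol amendment with IRB/IEC approval under section 23, and a flag on off-drug data. The visits and assessments are already in the schedule, but the few subjects who would otherwise have been closed early will attend up to two visits that they would have missed.
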